- **Pre ADAb negative – treatment emergent ADAb negative (Category 1):**
 - Considering AS0009 data only (Category 1a): includes subjects who are negative at AS0008 Baseline and ADAb negative at all sampling points in AS0009 (including SFU).
 - Considering AS0008 and AS0009 data (Category 1b): includes subjects who are negative at AS0008 Baseline and ADAb negative at all sampling points in AS0008 and AS0009 (including AS0009 SFU).

- **Pre ADA_b negative – treatment emergent ADA_b positive (Category 2):**
 - Considering AS0009 data only (Category 2a): Includes subjects who are negative at AS0008 Baseline and ADA_b positive at any sampling point in AS0009 (up to and including SFU and including the AS0009 EV). This group also includes subjects who have a missing pre-treatment sample (either missing or insufficient volume) at AS0008 Baseline with one or more ADA_b positive samples in AS0009.
 - Considering AS0008 and AS0009 data (Category 2b): Includes subjects who are negative at AS0008 Baseline and ADA_b positive at any sampling point post treatment in AS0008 and/or AS0009 (up to and including AS0009 SFU). This group also includes subjects who have a missing pre-treatment sample (either missing or insufficient volume) at AS0008 Baseline with one or more ADA_b positive samples in AS0008 or AS0009.
- **Pre ADA_b positive – treatment emergent reduced ADA_b (Category 3):**
 - Considering AS0009 data only (Category 3a): Includes subjects who are positive at AS0008 Baseline, and ADA_b negative at all sampling points in AS0009 (including SFU).
 - Considering AS0008 and AS0009 data (Category 3b): Includes subjects who are positive at AS0008 Baseline, and ADA_b negative at all sampling points in AS0008 and AS0009 (including SFU).
- **Pre ADA_b positive – treatment emergent unaffected ADA_b positive (Category 4):**
 - Considering AS0009 data only (Category 4a): Includes subjects who are positive at AS0008 Baseline and are positive at any sampling point in AS0009 (including SFU) with titer values of the same magnitude as AS0008 Baseline (i.e. less than a predefined fold increase from the AS0008 Baseline value defined within the validation of the assay).

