Summaries of AEs in AS0008 and AS0009 will include AEs with onset on the first dose of bimekizumab in AS0008 up to 140 days after the last dose of bimekizumab in AS0009. AEs which occur on the day of a treatment switch will be considered to have begun on the previous treatment, with the exception of the following AEs which will be considered to have begun on the new treatment:

- Events that fulfill the anaphylaxis criteria for acute events (see [Section 10.2.3](#)).
- Events that fulfill the hypersensitivity reaction criteria for (see [Section 10.2.3](#)).
- Events with a HLT of “Administration site reactions NEC”.
- Events with an HLT of “Injection site reactions”.

AEs which occur on the first day of bimekizumab treatment in AS0008 following initial treatment with placebo will not be included in the summaries, unless they fulfill 1 of the 4 exception criteria above. AEs which occur after the last dose of bimekizumab in AS0009 and up to 140 days after the last dose of bimekizumab in AS0009 will be assigned to bimekizumab 160mg.

AEs will be presented as “number of subjects (percentage of subjects) [number of events]”. “[number of events]” will include all cases of an AE including repeat occurrences in individual subjects, while “number of subjects” will count each subject only once.

An overview of TEAE (number and percentage of subjects with any TEAE, serious TEAE, TEAE leading to study discontinuation, TEAE leading to permanent withdrawal of study medication, drug-related TEAE, severe TEAE, fatal AE [see note below], fatal TEAE and TEAE with missing seriousness) will be provided by treatment group at completion of AS0008 and overall. This summary will be repeated by SS Sub-population. It will also be repeated including all TEAEs in AS0008 and AS0009 reported for subjects in the AS0009 SS (with the exception of those with onset during placebo treatment) combined.

The category for fatal AEs will be based on all subjects enrolled in AS0009 in all the above summaries.

The following categories of TEAE will be summarized by MedDRA SOC, HLT and PT, including EAIR and EAER (calculated as described in [Section 10.2.2](#)), where all summaries refer to AEs reported in AS0009 only except where stated:

- All TEAEs by treatment group at completion of AS0008 and overall.
- All TEAEs by treatment group at completion of AS0008 and overall, by SS Sub-population.
- Serious TEAEs by treatment group at completion of AS0008 and overall.

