- Serious TEAEs by treatment group at completion of AS0008 and overall, by SS Sub-population.
- All TEAEs in AS0008 and AS0009 by treatment at time of AE onset (BKZ 160mg, BKZ 320mg and BKZ Total).
- Serious TEAEs in AS0008 and AS0009 by treatment at time of AE onset (BKZ 160mg, BKZ 320mg and BKZ Total).

- All TEAEs AS0008 and AS0009 by timing of onset relative to ADAb status in AS0008 and AS0009. This will include columns for the following:
 - TEAEs starting before the first ADAb positive result in AS0008 and AS0009 (includes ADAb Categories 2b only)
 - TEAEs starting on the same date or after the first ADAb positive result in AS0008 and AS0009 (includes ADAb Categories 2b, 3b, 4b, 5b and 6b)
 - TEAEs for subjects who are ADAb negative at all time points in AS0008 and AS0009 (includes ADAb Categories 1b only)

Note that any TEAEs occurring for a subject who was ADAb positive at AS0008 Baseline will therefore all occur after ADAb positivity; such subjects will be excluded from the first column in the above table. Subjects in Category 9b (missing) will not be included in the table.

The following categories of TEAE will be summarized by MedDRA SOC, HLT and PT, by treatment group at completion of AS0008 and overall:

- TEAEs leading to study discontinuation and/or permanent withdrawal of study medication.
- TEAEs leading to permanent withdrawal of study medication.
- TEAEs with a fatal outcome.
- All TEAEs by maximum relationship.
- Serious TEAEs by maximum relationship.
- TEAEs with a fatal outcome by maximum relationship.
- All TEAEs by maximum intensity.
- Non-serious TEAEs reported by more than the reporting threshold of 5% of subjects. The cut-off will be applied before rounding on each treatment group and overall.

A further summary will be presented by treatment group at completion of AS0008 and overall displaying the frequency of TEAEs by descending frequency of PT.

An additional table will be presented by MedDRA SOC, HLT and PT, by treatment at time of AE onset (BKZ 160mg, BKZ 320mg and BKZ Total) for all TEAEs in AS0009 and all TEAEs that were ongoing from AS0008 at the time of the AS0009 EV. Ongoing TEAEs are defined as TEAEs that started prior to the AS0009 EV and continued after the first dose of study medication in AS0009.

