10.2.1 Adverse event duration and time since first/last dose

Missing start or end dates will be imputed as described in [Section 4.2.2](#) prior to any calculation described in this section.

The duration of each AE will be calculated as follows:

$$\text{Duration (days)} = \text{date of outcome} - \text{date of onset} + 1 \quad (15)$$

The time since first bimekizumab dose for each TEAE will be calculated three times for each of the reference dates below:

- Relative to the date of first administration of bimekizumab in AS0008.
- Relative to the date of the first dose of bimekizumab 160mg, only for AEs with onset during treatment with bimekizumab 160mg OR
- Relative to the date of the first dose of bimekizumab 320mg, only for AEs with onset during treatment with bimekizumab 320mg.
 - For these criteria during treatment refers to TEAEs with onset up to 140 days after the last dose on that treatment.
- Relative to the start date of study medication in AS0009.

Time since first dose will be calculated as follows for AEs occurring on or after the reference date (as defined above):

$$\begin{aligned} \text{Time since first BKZ dose (days)} \\ = \text{Date of AE onset} - \text{Reference date} + 1 \end{aligned} \quad (16)$$

The time since most recent bimekizumab dose for each TEAE will be calculated as follows for AEs occurring on or after the reference date (as defined above):

$$\begin{aligned} \text{Time since most recent BKZ dose (days)} \\ = \text{Date of AE onset} \\ - \text{Date of most recent dose prior to AE} + 1 \end{aligned} \quad (17)$$

For any AE occurring on the same day as a given dosing occasion the most recent dose will be considered to be the dose given on the same day i.e., time since most recent dose would be equal to 1 for all such AEs.

For AEs occurring prior to the reference date (as defined above) the time since dosing will be calculated as follows for first/most recent BKZ dose:

$$\text{Time since BKZ dose (days)} = \text{Date of AE onset} - \text{Reference date} \quad (18)$$

Days on treatment at AE onset will be calculated three times using the same three reference dates as for time since first dose. Days on treatment at AE onset will be calculated as:

$$\begin{aligned} \text{Days on treatment at AE onset} \\ = \text{Date of last or latest dose prior to AE onset} \\ - \text{Reference date} + 1 \end{aligned} \quad (19)$$

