10.2.2 Exposure-adjusted incidence rate and exposure-adjusted event rate

The time at risk (in days) at AE onset is the same as the time since first bimekizumab dose as described in [Section 10.2.1](#).

Total time at risk (as defined in [Section 10.1](#)) and time at risk at AE onset will be divided by 365.25 to give years at risk.

EAIR and EAER will be calculated separately for tables including all events in AS0008 and AS0009 combined, and for tables including events with onset in AS0009 only. The former tables will use time at risk relative to the start date of bimekizumab 160mg or 320mg (for the ‘BKZ 160mg’ and ‘BKZ 320mg’ columns) and time at risk relative to the date of the first dose of bimekizumab (for the ‘BKZ Total’ column). The latter table will use time at risk relative to the start date of study medication in AS0009.

The EAIR is defined as the number of subjects with a specific AE adjusted for the exposure and will be scaled to 100 patient-years:

$$\frac{EAIR = 100 * n_{AE}}{\sum_{i=1}^{n_{AE}} T_{Exp,i} + \sum_{j=1}^{n_{noAE}} T_{Risk,j}} \quad (20)$$

Where n_{AE} is the number of subjects with the AE, $T_{Exp,i}$ is a subject’s time at risk at AE onset in years (equation [15] in years) and $T_{Risk,j}$ is the time at risk in years for subjects who did not experience the AE of interest.

If a subject has multiple events at the level of coding evaluated, the time at risk at AE onset is calculated to the first occurrence of the AE.

Exact Poisson 95% CIs for incidence rates are calculated using the relationship between the Poisson and the chi-square distribution (Ulm, 1990; Fay and Feuer, 1997):

$$LCL = \frac{\chi^2_{2n,\frac{\alpha}{2}}}{2} \quad (21)$$

$$UCL = \frac{\chi^2_{2(n+1),1-\frac{\alpha}{2}}}{2} \quad (22)$$

$$CI_{Lower} = 100 * \frac{LCL}{\sum_{i=1}^{n_{AE}} T_{Exp,i} + \sum_{j=1}^{n_{noAE}} T_{Risk,j}} \quad (23)$$

$$CI_{Upper} = 100 * UCL \frac{UCL}{\sum_{i=1}^{n_{AE}} T_{Exp,i} + \sum_{j=1}^{n_{noAE}} T_{Risk,j}} \quad (24)$$

where n_{AE} is the number of subjects with the AE and is the basis for the number of the degrees of freedom for the chi-square quantile for the upper tail probability χ^2 , $T_{Exp,i}$ is a subject's time at risk at AE onset in years, n_{noAE} the number of subjects without the specific AE and $T_{Risk,j}$ the total time at risk for subjects who did not experience the AE.

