The EAER is defined as the number of AEs reported up to 140 days after last dose, including repeat occurrences in individual subjects, and adjusted for exposure, and will be scaled to 100 subject-years:

$$\frac{EAER = 100 * N_{AE}}{\sum_{j=1}^{n_{All}} T_{Risk,j}} \quad (25)$$

where N_{AE} is the total number of AEs, $T_{Risk,j}$ is a subject's total time at risk in years and n_{All} the number of subjects.

No CI will be computed for EAER.

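### The table of TEAEs before and after the first ADAb-positive result splits events at that date but gives no split of time at risk; on the literal EAER formula both columns come out too low

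*SAP*

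**What the plan says.** SAP Section 10.2 lists TEAE tables that "will be summarized by MedDRA SOC, HLT and PT, including EAIR and EAER (calculated as described in" Section 10.2.2. One of them covers AS0008 and AS0009 combined and has three columns by ADAb status:

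- "TEAEs starting before the first ADAb positive result in AS0008 and AS0009 (includes ADAb Categories 2b only";
- events on or after the first positive result, for Categories 2b to 6b;
- events of subjects negative throughout (Category 1b).

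A note adds that subjects positive at AS0008 Baseline are left out of the first column. Section 9.2 defines Category 2b as negative (or missing) at AS0008 Baseline and "positive at any sampling point post treatment in AS0008 and/or AS0009 (up to and including AS0009 SFU" visit.

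On time at risk:

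- Section 10.2.2: "The time at risk (in days) at AE onset is the same as the time since first bimekizumab dose".
- Section 10.2.1: "The time since first bimekizumab dose for each TEAE will be calculated three times for each of the reference dates below". None of those reference dates is an ADAb date.
- Section 10.2.2, for the combined tables: "The former tables will use time at risk relative to the start date of bimekizumab 160mg or 320mg", with first bimekizumab dose for the Total column. AS0009-only tables start at first AS0009 dose. No clock is named for an ADAb column.
- Equation 25 divides the number of events by the sum of each subject's "total time at risk in years".
- For EAIR with repeated events, "the time at risk at AE onset is calculated to the first occurrence of the AE".
- Table 10-2 ends time at risk at last dose plus 140 days or at last clinical contact, whichever is earlier, with death handled separately.

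For the COVID-19 periods, Section 10.2.4 and Table 10-5 do set out time at risk period by period.

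**The concern.** A rate needs numerator and denominator over the same period. Here a Category 2b subject's events go to one column or the other by date, while the formula that the table is referred to uses the subject's whole time at risk. Each column then has part of the events over all of the time.

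This is the one table that sets exposure-adjusted TEAE rates against ADAb timing. If the true rate is the same before and after, the contrast between the columns will show how early subjects turned positive, not any change in risk. Early conversion would look like a rise in events after positivity, and late conversion like a fall. Both columns would also look low beside the ADAb-negative column, whose subjects need no split.

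**Working it through.** The plan states no rate for this table, so there is no figure to reproduce. The check applies the formulas as they stand and then with time split.

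**Inputs from the documents.** AS0008 runs 48 weeks to AS0009 entry, AS0009 treatment up to 204 weeks, and the at-risk window 140 days after last dose (20 weeks).

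**Assumptions.** Completer on bimekizumab from the start of AS0008; constant event rate λ; common first-positive time s, in weeks since first bimekizumab dose (48 is about AS0009 entry, 144 about AS0009 Week 96). The documents give neither event rates nor seroconversion times.

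**Time at risk.** T = (272 × 7 + 1)/365.25 = 1905/365.25 = 5.216 years. Before: s. After: u = T − s.

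**EAER, full time in both columns.** Before = λs/T and after = λu/T, so the multipliers s/T and u/T do not depend on λ. At λ = 20 per 100 patient-years (PY):

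| First positive (weeks) | s/T | u/T | EAER before | EAER after |
|---|---|---|---|---|
| 12 | 0.04 | 0.96 | 0.9 | 19.1 |
| 48 | 0.18 | 0.82 | 3.5 | 16.5 |
| 96 | 0.35 | 0.65 | 7.1 | 12.9 |
| 144 | 0.53 | 0.47 | 10.6 | 9.4 |

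Per 100 such subjects at 48 weeks: 18.4 events in 92.0 PY before and 85.9 events in 429.6 PY after. Both are divided by 521.6 PY. The after/before ratio, truly 1, becomes 0.82/0.18, about 4.7. At 144 weeks it is 0.89. At 252 weeks (AS0009 Week 204) it is 141 days/1764 days = 0.08. With time split at s, both columns return 20.

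**Dilution by baseline-positive subjects.** If they are a share w of the second column, its EAER is λ[(1 − w)u + wT]/T. For w = 25% and 50% this gives 17.4 and 18.2 (48 weeks), or 12.1 and 14.7 (144 weeks).

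**EAIR.** Section 10.2.2 points time at AE onset to equation 15, which is AE duration; I read it as equation 16, time since first dose. Let M(x) = [1 − e^(−λx)(1 + λx)]/λ, p = 1 − e^(−λs), q = 1 − e^(−λu), with λ per year.

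- Before = p/[M(s) + (1 − p)T].
- After, first occurrence taken within the period = q/[qs + M(u) + (1 − q)T].
- After, first occurrence taken over any period = q/[qM(s) + (1 − p)(qs + M(u)) + (1 − q)T].

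At 48 weeks and λ = 0.20: before 0.168/(0.075 + 4.339) = 3.8 per 100 PY; after 15.2 or 16.1. At λ = 1.00: before 26.0; after 51.7 or 95.4, against a true 100. The error therefore depends on the event rate and on how first occurrence is read, which the SAP does not settle. For a very common term the second column can be nearly right.

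**The case against.** **The SAP is silent rather than wrong.** Section 10.2.2 names no clock for any ADAb column, so a programmer might split the time unprompted. This stands in part: full time in both columns is the literal reading of equation 25, not an instruction written for this table. But Section 10.2 sends the table to Section 10.2.2, whose only EAER formula uses total time. Where the SAP splits person-time elsewhere it says so: Table 10-2 by dose and Table 10-5 by COVID-19 period. If the text is taken as silent, the rates are undefined and a rule is still needed.

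**A reader might infer that time at risk rests on dose dates alone.** It does not: Table 10-2 also uses last clinical contact and death. None of these is an ADAb date, so the point is unchanged.

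**Splitting the time does not make the columns fully comparable.** This stands. A Category 2b subject must stay in the study until a later positive sample, so a fatal or withdrawal-causing event will generally not appear in the first column. From AS0009 Week 48 to Week 192, samples are 24 weeks apart (SAP Section 2.2.5), so conversion is dated only to an interval. Equal rates after the split also rest on the constant-rate assumption.

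**The table is minor.** This stands as to weight. It is supplementary and descriptive, and protocol Section 13.3.1 asks for these rates by lead-in treatment group, not by ADAb status.

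**Conclusion.** The point holds for this one table. On the literal reading of equation 25, EAER is too low in both Category 2b columns whenever those subjects have time and events on both sides of the first positive date. That direction is algebraic and needs no assumed rate. The size does need assumptions: 0.18/0.82 at 48 weeks and 0.53/0.47 at 144 weeks hold for a completer on bimekizumab from the start of AS0008, with Category 2b subjects only. Actual seroconversion times and the share of baseline-positive subjects are not given. EAIR is generally too low as well, by an amount that cannot be fixed from the documents.

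Two stronger conclusions are not supported. One is that the plan's TEAE rates in general are affected: the main tables do not cut a subject's events at an ADAb date. The other is that the counts and percentages in this table are a sound before/after comparison because they use no denominator time. They are calculated correctly, but they carry the same unequal follow-up: 18.4 against 85.9 events per 100 subjects at 48 weeks with no difference in risk. The rule should be added, in proportion to one supplementary display.

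**What to change.** Add to Section 10.2.2 a rule for this table in the style of Table 10-5:

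- **Before (Category 2b):** first bimekizumab dose to the day before the first positive sample, not below zero and not past the end of the Table 10-2 at-risk window.
- **On/after:** from the later of first positive sample and first bimekizumab dose (first bimekizumab dose if baseline-positive) to the end of that window; zero if the first positive falls beyond it.
- **ADAb-negative:** from first bimekizumab dose to the end of the window.
- **Time at AE onset for EAIR:** from the start of the period to the first occurrence within that period.

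The floor and the later-of rule cover the two sequences that start on placebo. If a sample were positive at AS0008 Week 8, before bimekizumab at Week 12, an unguarded rule would give −4 weeks before and 4 weeks of placebo time after, although placebo-onset events are excluded. AS0008 sampling dates are not in the documents, so this is a precaution. The cap is needed because the SFU sample may be taken up to day 147 after last dose, against a 140-day window.

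Footnote that the first column is conditional on remaining in the study until a later positive sample, and that conversion is known only to the sampling interval.

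Dropping EAIR and EAER from this table is a fallback; Section 10.2 already limits another TEAE table to n and %. It removes the wrong rates but not the unequal follow-up behind the counts, so it too needs a footnote.

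Cost: a short SAP rule and reprogrammed denominators for one table, from dates already collected.

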13.3 Planned safety analyses

13.3.1 Safety analyses

Safety variables will be analyzed for all subjects in the SS.

Adverse events will be coded according to the Medical Dictionary for Regulatory Activities.

Adverse events will be summarized descriptively by treatment group at completion of the lead-in study, primary system organ class, high level term, and preferred term. This summary will include raw incidence rates, exposure adjusted incidence rate (EAIR) with associated 95% confidence interval, and the exposure adjusted event rate (EAER), where the EAIR and EAER are expressed per 100 patient-years of exposure.

Patient exposure at risk in days will be defined as date of last administration of bimekizumab - date of first administration of bimekizumab +20 weeks. If a subject has an adverse event with fatal outcome, patient exposure at risk is censored at the date of death.

The extent of exposure to IMP in AS0009 will be summarized using descriptive statistics by treatment group at AS0009 entry.

Change from AS0009 entry values in laboratory and vital signs variables will be summarized descriptively by visit and by treatment group at completion of the lead-in study.

The results of the eC-SSRS will be summarized by visit and by treatment group at completion of the lead-in study using number of subjects and percentages with events in: each of the eC-SSRS questions, suicidal behavior, suicidal ideation, suicidal behavior and ideation, and self-injurious behavior without suicidal intent.

All safety analyses will be conducted for both subpopulations.

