2.2 Study variables

2.2.1 Safety variables

2.2.1.1 Primary safety variables

The primary safety variables are the incidences of treatment-emergent adverse events (TEAEs) and treatment-emergent serious adverse events (SAEs). The latter is measured by the incidence of serious TEAEs.

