2.2.1.2 Secondary safety variables

The secondary safety variable is the withdrawal from the study due to TEAEs. This is measured by the incidence of TEAEs leading to study discontinuation and/or permanent withdrawal of study medication.

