2.2.1.3 Other safety variables

Other safety variables are:

- Change from AS0009 Laboratory Baseline (as defined in [Section 3.3](#)) in clinical laboratory variables (hematology and biochemistry, with the exception of high-sensitivity C-reactive protein [CRP]) at each visit (AS0009 Week 24, 36, 48, 60, 72, 84, 96, 108, 120, 132, 144, 156, 168, 180, 192, 204, 208, SFU).
- Change from AS0008 Baseline in vital signs (pulse, temperature and blood pressure) (AS0009 Entry Visit [EV], Week 4, 8, 12, 24, 36, 48, 60, 72, 84, 96, 108, 120, 132, 144, 156, 168, 180, 192, 204, 208, Completion/ET, SFU) and body weight (AS0009 EV, Week 12, 24, 36, 48, 60, 72, 84, 96, 108, 120, 132, 144, 156, 168, 180, 192, 204, 208, SFU).

Note that the change from AS0009 EV variables specified in the protocol will not be reported, since the EV assessment is made after 36 or 48 weeks of bimekizumab treatment and there is unlikely to be any further important change.

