10.2.4 Impact of COVID-19

In order to assess the impact of the COVID-19 global pandemic on the primary safety endpoint of incidence of TEAEs and serious TEAEs, additional listings and summaries will be presented.

For reporting purposes AEs will be assigned to ‘Prior to COVID-19 pandemic’, ‘During the COVID-19 pandemic’ or ‘Post the COVID-19 pandemic’ based on the following:

- If the date of AE onset (based on imputed start date) is prior to 11 March 2020 the AE will be assigned as ‘Prior to COVID-19 pandemic’
- If the date of AE onset (based on imputed start date) is on or after 11 March 2020 the AE will be assigned as ‘During the COVID-19 pandemic’
 - The date of 11 March 2020 is chosen as the date the World Health Organization declared COVID-19 as a pandemic.

- If the date of AE onset (based on imputed start date) is after the date on which the World Health Organization declares the end of the COVID-19 pandemic the AE will be assigned as ‘Post the COVID-19 pandemic’
 - If the date of the end of the COVID-19 pandemic is on or after the date of last subject, last visit, the ‘Post the COVID-19 pandemic’ phase will not apply.

The following categories of TEAE will be summarized by MedDRA SOC, HLT and PT, including EAIR and EAER:

- All TEAEs by time of onset relative to COVID-19 pandemic (‘Prior to COVID-19 pandemic’, ‘During the COVID-19 pandemic’ and ‘Post the COVID-19 pandemic’)
- All serious TEAEs by time of onset relative to COVID-19 pandemic (‘Prior to COVID-19 pandemic’, ‘During the COVID-19 pandemic’ and ‘Post the COVID-19 pandemic’)
- All COVID-19 related TEAEs by treatment at completion of AS0008 and overall
 - COVID-19 related TEAEs will be identified based on the verbatim term including the text string ‘COVID’. These will include confirmed or suspected COVID-19 infections.

TEAEs leading to study discontinuation and/or permanent withdrawal of study medication will be summarized by MedDRA SOC, HLT, and PT, and by time of onset relative to COVID-19 pandemic (‘Prior to COVID-19 pandemic’, ‘During the COVID-19 pandemic’ and ‘Post the COVID-19 pandemic’).

A separate listing of all COVID-19 related AEs will be presented, where COVID-related AEs are identified as described above. In addition, the time of onset of each AE relative to the COVID-19 pandemic will be flagged in all AE listings.

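### Of the primary and secondary safety variables, only withdrawal due to TEAEs is listed without an exposure-adjusted rate or confidence interval, in its main table and in its pandemic-period table

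*SAP*

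**What the plan says.** SAP 2.2.1.1 names two primary safety variables, the incidences of TEAEs and of serious TEAEs. SAP 2.2.1.2 names one secondary safety variable: "The secondary safety variable is the withdrawal from the study due to TEAEs". It adds: "This is measured by the incidence of TEAEs leading to study discontinuation and/or permanent withdrawal of study medication".

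Protocol 13.3.1 describes the adverse event summary in general terms: "This summary will include raw incidence rates, exposure adjusted incidence rate (EAIR) with associated 95% confidence interval", together with the exposure-adjusted event rate (EAER). The opening of SAP section 10 says the same and exempts no table.

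SAP 10.2 then sets out two lists. The first is introduced by "The following categories of TEAE will be summarized by MedDRA SOC, HLT and PT, including EAIR and EAER" and holds all TEAEs and serious TEAEs, with their repeats. The second has no such wording, and its first entry is "TEAEs leading to study discontinuation and/or permanent withdrawal of study medication". The default display in 10.2 is number of subjects, percentage and number of events.

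SAP 10.2.4 follows the same pattern. All, serious and COVID-19 related TEAEs get EAIR and EAER. A separate sentence covers withdrawals, with no mention of a rate: "TEAEs leading to study discontinuation and/or permanent withdrawal of study medication will be summarized by MedDRA SOC, HLT, and PT, and by time of onset".

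Table 10-5 already defines each subject's time at risk in each pandemic period. SAP 3.10, which lists changes from the protocol analyses, is silent on the point.

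**The concern.** Follow-up in this extension runs from early dropout to 224 weeks. A raw percentage mixes the risk of withdrawal with the length of observation, which is presumably why the plan adjusts the two primary variables for exposure. The one secondary safety variable would be left with no rate and no statement of precision.

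The by-period table is the more serious case. SAP 3.10.1 names study withdrawal due to TEAEs among the three endpoints whose pandemic impact is to be investigated, yet it is the only one of the three without the adjustment that Table 10-5 provides. The periods are cut at calendar dates, so their length depends on when each subject entered.

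The denominator is also unsettled. The rule in 10.2.4 that limits each period to subjects still at risk is given for calculating EAIR and EAER. Without those rates, the general rule in SAP 3.1 bases percentages on the analysis set. Subjects who left before 11 March 2020 could then stay in the During denominator although they can no longer have the event.

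**Working it through.** **1. Tables side by side.** The documents give no planned rate or precision for this variable, so there is no figure to reproduce.

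| Variable (SAP 2.2.1) | Main table, SAP 10.2 | By-period table, SAP 10.2.4 |
|---|---|---|
| All TEAEs (primary) | EAIR, EAER | EAIR, EAER |
| Serious TEAEs (primary) | EAIR, EAER | EAIR, EAER |
| TEAEs leading to withdrawal (secondary) | none listed | none listed |

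**2. Bounds on period length for a subject who stays on study.**
- Maximum follow-up is 204 + 20 = 224 weeks (SAP section 2).
- The shortest Prior period is 48 weeks, since SAP 8.5 says the pandemic began after all subjects had completed Week 48.
- The longest possible Prior period runs from 15 May 2017, the final protocol date in SAP section 1, to 10 March 2020. That is 1,031 days, and 1,031/7 = 147 weeks. It is a ceiling, not an estimate, because entry dates are not given.
- During = 224 − Prior, assuming that the pandemic ends after follow-up.

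**3. Raw percentages under an unchanged rate.** Percentage = 100 × [1 − exp(−r × weeks × 7/365.25)], with r = 0.03 per year **assumed** in both periods and percentages taken among subjects at risk when each period starts.

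| Prior / During (weeks) | Prior | During | Ratio |
|---|---|---|---|
| 48 / 176 | 2.7% | 9.6% | 3.5 |
| 80 / 144 | 4.5% | 7.9% | 1.8 |
| 112 / 112 | 6.2% | 6.2% | 1.0 |
| 147 / 77 | 8.1% | 4.3% | 0.53 |

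With r from 1 to 5 per 100 patient-years (PY), the extreme ratios hardly move: 3.62 to 3.45 at 48/176 and 0.53 to 0.54 at 147/77.

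**4. What a rate would add.** SAP 10.2.2 gives EAIR = 100 × n/PY, with limits 100 × [χ²(0.025; 2n)/2]/PY and 100 × [χ²(0.975; 2(n+1))/2]/PY. Take an **assumed** n = 26 of 285 subjects. The raw figure is 26/285 = 9.1% whatever the exposure. Exposure is also assumed:

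| Exposure | EAIR per 100 PY (95% CI) |
|---|---|
| 285 × 1.5 years = 428 PY | 6.08 (3.97 to 8.91) |
| 285 × 3 years = 855 PY | 3.04 (1.99 to 4.46) |
| 285 × 224 × 7/365.25 = 1,223 PY | 2.13 (1.39 to 3.11) |

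The same percentage is compatible with nearly a threefold range of rates (6.08/2.13 = 2.9).

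**5. Effect of the 140-day tail.** Time at risk in Table 10-2 runs up to 140 days (20 weeks) past the last dose. For a completer that is 20/224 = 9% of the total. For someone whose last dose is at Week 24, it is up to 20/(24 + 20) = 45%.

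**The case against.** The strongest reply is that the omission is inferred. The opening of SAP section 10 states a general rule that could cover every adverse event table, and where 10.2 wants a bare table, for TEAEs ongoing from AS0008, it says so. This stands in part. It turns the point into an inconsistency between the general rule and the lists, but a programmer working from the lists would still produce counts and percentages.

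A reader might infer a plain departure from the protocol. Protocol 13.3.1 can be read as describing only the overall adverse event summary, and a number and percentage is an incidence in the sense of SAP 2.2.1.2. A reader might also infer that this is the only named safety variable of any kind without a rate or interval. It is not: laboratory, vital-sign and body-weight changes (SAP 2.2.1.3) have none, though as continuous changes they need none, and neither do fatal TEAEs or the eC-SSRS incidences.

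For the main table, bracketed event counts and the total time at risk in SAP 10.1 would let a reader form a crude rate. That is fair, but the exposure summaries in 10.1 are not split by pandemic period, so it does not help the by-period table. The study is also single-arm and descriptive, with no formal comparison planned. That limits the weight of the point, although a table by period invites comparison.

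Finally, the 140-day tail includes time when study medication can no longer be withdrawn, so the EAIR would be somewhat diluted, more so where early non-AE dropout is common. This stands as a caveat on the fix.

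**Conclusion.** The point holds as a minor correction. Withdrawal due to TEAEs is the only primary or secondary safety variable whose listed tables carry no EAIR or 95% interval. That conflicts with the plan's general rule, and no reason is recorded.

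The practical harm lies in the by-period table. With no change in risk, raw percentages could show anything from about a 3.5-fold rise to a near-halving. This range rests on an assumed constant rate, follow-up to 224 weeks, a pandemic end after follow-up, and outer bounds on entry dates. A reader might infer that the table would show a fall, or a rise, during the pandemic. The documents support neither, because they give no entry dates and no pandemic end date, and at an even split of 112/112 weeks there is no distortion.

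**What to change.** In SAP 10.2, add EAIR with the exact Poisson 95% interval of 10.2.2 to the table of TEAEs leading to study discontinuation and/or withdrawal of study medication. In SAP 10.2.4, add the same to its by-period table, using the Table 10-5 time at risk and counting only subjects at risk in each period. EAER is optional, since this event usually occurs once per subject.

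Add a footnote that time at risk includes up to 140 days after the last dose. Alternatively, repeat the rate as a check with an on-treatment denominator based on the Table 10-1 duration. If the sponsor prefers to leave the rate out, the omission and its reason belong in SAP 3.10.

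The cost is a small text change and extra columns in two tables. The formulas and time-at-risk definitions already exist; only the optional on-treatment check would need some added programming.
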